As a part of our original Patient-Centered Outcomes Research Institute (PCORI) proposal, we planned to educate nurses to address the observed deficiencies and misconceptions and improve their ability to communicate effectively with patients. Historically, nurse education has been done via a linear, PowerPoint-based platform with voice-over but with no interactive component (Static). A newer platform for nurse education became available for use and includes scenario-based teaching, ongoing assessment, and immediate remediation. Most importantly, it is a highly interactive product (Dynamic).

Study Objectives and Hypotheses

The Objective of this study is to improve knowledge about the benefits and importance of VTE prophylaxis and harms associated with VTE with the goal of decreasing non-administration of prescribed VTE prophylaxis.

- Primary Hypothesis: Nurse participants who receive either of these interventions will improve administration of prescribed VTE prophylaxis evidenced by a decrease in frequency of non-administered doses of VTE prophylaxis, compared with their frequency at baseline.
- Secondary Hypothesis: Nurse participants who receive the Dynamic education format will have a larger decrease in frequency of missed doses of VTE prophylaxis compared with those who participate in the Static education format.

2. Study Design

A. Study Design

- a. Cluster randomized trial

B. Study setting: Johns Hopkins Hospital, Baltimore MD

C. Eligibility Criteria

- a. All nurses permanently assigned to one of the 21 included study floors

D. Interventions

- a. Education A: An interactive dynamic learner-centric scenario-based education module with ongoing assessment, and immediate remediation (Dynamic).
- b. Education B: A linear static PowerPoint-based platform with voice-over but with no interactive component (Static).

Participants will be assigned one of two education modules based on their permanent floor assignment. The same education type will be assigned to all nurses on a single floor to mitigate issues related to contamination if nurses discuss the education with their colleagues.

E. Enrollment

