- a. Nurses will be identified using our centralized education directory that associates nurses with their designated departments and hospital floors. All nurses permanently assigned to one of the 21 included study floors will be included in this study. Nurses who are not permanently associated with one of the 21 hospital floors (e.g. traveling nurse, float nurse) will be excluded from this study.

F. Randomization

- a. Nurses will be identified using our centralized education directory that associates nurses with their designated departments and hospital floors. Nurses will be cluster randomized by floor to receive one of two education modules about VTE prevention. Because of known differences between medical and surgical floors in VTE prophylaxis administration practice and culture, floors were stratified by department (i.e. medicine and surgery) for randomization. Within strata, we will use a coin toss to randomize floors into study arms.

G. Duration of Study

- a. Nurses will be given three months to complete the assigned education module. Data will be collected for one full year to include medication administration practice at baseline, during the education trial, and after the education trial.

H. Outcomes

- a. Primary Outcome measure: Proportion of non-administered doses of pharmacological VTE prophylaxis (dose level)
- b. Secondary Outcome Measures:
 - i. Nurse-reported relevance of and satisfaction with the education modules
 - ii. Proportion of doses documented as missed due to patient refusal (dose level)
 - iii. Proportion of patients with any VTE (patient level)
 1. VTE are defined by AHRQ PSI-12 diagnosis codes
 - iv. Proportion of patients with Deep Vein Thrombosis (DVT) (patient level)
 - v. Proportion of patients with Pulmonary Embolism (PE) (patient level)

Patient demographic data will be extracted from the Johns Hopkins Hospital administrative database. Pharmacologic VTE prophylaxis medication administration data will be extracted directly from electronic medication administration record in our computerized provider order entry system. Immediately following completion of the assigned education module, nurses will be asked to complete a voluntary 5-question survey to assess the relevance of and satisfaction with the education module.

3. Analytic methods

A. Baseline Characteristics

- a. Comparison of both arms to ensure similarity at baseline

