- b. Descriptive analysis of baseline characteristics i.e. simple counts and proportions by trial arm

B. Multi-level mixed effects linear regression

Due to the complexity of the multilevel structure of the data (i.e. multiple doses per patient across various hospitalizations, nurses and floors), multiple imputation¹⁹ will be used to reduce the levels of hierarchical structure to the floor level and nurse level by randomly selecting one dosage per patient. By reiterating the procedure 1000 times, we will estimate the odds ratios (ORs) and 95% confidence intervals conditional on the floor and nurse.

- a. Primary analyses: Intent-to-Treat
- b. Secondary analyses
 - i. Per protocol: Nurses who complete the education where the date of completion serves as an individual inflection point for pre-post education
 - ii. Nurse-reported relevance of and satisfaction with the education modules will be analyzed using a two-sided Chi-squared test

References

1. US Department of Health and Human Services. The Surgeon General's Call to Action to Prevent Deep Vein Thrombosis and Pulmonary Embolism. <http://www.ncbi.nlm.nih.gov/books/NBK44178/>. Accessed April 5, 2014.

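### The dose model in section 3.B names no patient covariate, so a change in patient mix within floors between periods would be mixed into the before-after odds ratio

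*Combined protocol and SAP*

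**What the plan says.** All references are to the combined protocol and SAP.

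- **Study Objectives and Hypotheses.** The primary hypothesis concerns nurses given either module and is "evidenced by a decrease in frequency of non-administered doses of VTE prophylaxis, compared with their frequency at baseline". The secondary hypothesis is that the Dynamic group "will have a larger decrease in frequency of missed doses of VTE prophylaxis compared with those who participate in the Static education format".
- **2.C and 2.F.** Nurses come from 21 floors, allocated by coin toss; "floors were stratified by department (i.e. medicine and surgery) for randomization".
- **2.G.** "Data will be collected for one full year to include medication administration practice at baseline, during the education trial, and after the education trial". Nurses have three months to complete the module.
- **2.H.** "Patient demographic data will be extracted" from an administrative database. No use for them is stated there. Doses missed because the patient refused are a secondary outcome.
- **3.A.** The arms are compared at baseline, by "Descriptive analysis of baseline characteristics i.e. simple counts and proportions by trial arm". No comparison of patients between periods is planned.
- **3.B.** One dose per patient is drawn at random, the draw is repeated 1000 times, and "we will estimate the odds ratios (ORs) and 95% confidence intervals conditional on the floor and nurse". No fixed effects are listed, whether period, arm, department or patient. The per-protocol analysis is a pre-post comparison around each nurse's completion date, and it names no patient covariate either.

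**The concern.** Floors are randomised between two kinds of education, not between education and none. Randomisation therefore supports the Dynamic versus Static contrast but not the primary hypothesis, which is a change over time. The doses before and after education will largely have gone to different inpatients, and nothing in the design balances those patients across periods.

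The plan itself treats the patient as one reason a dose is missed, since refusal is a named outcome. Conditioning on floor and nurse removes stable differences between floors and nurses. It does not remove a change in who occupies a given floor. Drawing one dose per patient deals with clustering within patients and leaves the mix between periods as it was.

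At stake is the reading of the primary odds ratio: a change in patients could pass for an education effect, or hide one. As 3.A is written, such a change would not be displayed either.

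**Working it through.** **Is there a plan figure to reproduce?** No. The documents give no baseline rate, effect size, sample size or power. Every rate and share below is an assumption, used only to show scale.

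**Formula.** Let a share q of patients belong to a group with missed-dose rate h, and the rest have rate l. The overall rate is p = q·h + (1−q)·l. If q changes between periods and education does nothing, the crude odds ratio is [p1/(1−p1)] / [p0/(1−p0)].

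**Illustration 1.** Assume h = 18%, l = 10% and q = 30% at baseline. Then p0 = 0.30×0.18 + 0.70×0.10 = 0.124, with odds 0.1416. The last column compares ln(OR) in absolute value with |ln 0.85| = 0.1625, where 0.85 is an assumed true effect.

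| Shift in q | p1 | OR | Share of ln 0.85 |
|---|---|---|---|
| +2 points | 0.1256 | 1.015 | 9% |
| +5 points | 0.128 | 1.037 | 22% |
| +10 points | 0.132 | 1.074 | 44% |
| −10 points | 0.116 | 0.927 | 47% |

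The downward result is 0.927, not the exact reciprocal of 1.074 (0.931).

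**Illustration 2, milder.** Assume h = 12%, l = 10%, q = 30% and a 2-point rise. Then p0 = 0.106, p1 = 0.1064 and OR = 0.1191/0.1186, which is 1.004 before rounding of the odds. That is about 3% of ln 0.85.

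**Illustration 3, stronger.** Assume q falls from 40% to 30%. With rates of 8% and 16%, p goes from 0.112 to 0.104 and OR = 0.92. With rates of 8% and 25%, p goes from 0.148 to 0.131 and OR = 0.87.

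**Does conditioning on floor and nurse remove it?** The figures above are crude, so this was checked by simulation: 200 data sets, 21 floors, an assumed 20 nurses per floor, an assumed 12,000 patients with one dose each, and floor and nurse SDs of 0.4 on the logit scale. Rates were 8% and 16%, q fell from 40% to 30% on every floor, and the true education OR was 1. The logistic fits used floor indicators and the true nurse effect as an offset, which is ideal conditioning.

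- Floor and nurse only: mean OR 0.92; p < 0.05 in 29.5% of data sets.
- With the patient covariate added: mean OR 1.00; p < 0.05 in 4.0%.

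So conditioning on floor and nurse does not remove a shift that occurs within floors. The 29.5% depends on the assumed number of patients, the 10-point shift, and a covariate that captures the patient group perfectly.

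**Arm contrast.** With the same 40% to 30% shift in both arms, and baseline odds 1.3 times higher in one arm, the two before-after ORs are 0.9203 and 0.9206, a ratio of 1.000. With the shift in one arm only, the ratio is 0.92.

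**The case against.** **The text does not say that floor and nurse are the only terms.** A reader might infer that the plan has decided to exclude demographics. The documents do not support that. The sentence follows directly on reducing the hierarchy to floor and nurse, so it may simply name the clustering levels. Section 3.B lists no fixed effects at all, not even the period and arm terms that the hypotheses need. This stands: what can be said is that no patient covariate is named.

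**Nor do the documents say that demographics serve only a descriptive table.** Section 3.A does not say whether its baseline characteristics are those of patients, nurses or floors. This also stands; the extracted demographics have no stated role in the model, and no more can be claimed.

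**The mix may not shift.** This is fair. Mix that moves because volume moves between floors is already absorbed; only change within floor and nurse counts. Nothing in the documents shows that age or sex carries a difference as large as 18% against 10%, or that shares move by 10 points within a year. The plausible range includes negligible.

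**The arm contrast is randomised.** A reader might infer that it is biased too. It is not systematically so. A common shift nearly cancels, and a differential shift unrelated to education is chance imbalance among 21 floors.

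**Age and sex will not rescue a before-after design.** This is correct as well. Severity, reason for admission and calendar trend stay confounded with period. That limits what the adjustment can achieve but is no argument against a partial remedy on data already being collected.

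**Conclusion.** The point holds for the primary before-after hypothesis and for the per-protocol pre-post analysis. With no patient covariate named and no concurrent uneducated group, a change within floors in measured patient mix would be mixed into the primary odds ratio. It is a risk, not a demonstrated bias. Direction is unknown, and on assumed inputs the size runs from about 3% to nearly half of the log of an assumed OR of 0.85 (illustrations 1 and 2), and more under harsher assumptions. For Dynamic versus Static the benefit of adjustment is mainly precision and protection against chance imbalance. Age and sex are safe covariates, because nurse education cannot alter them. The change is worth making because it costs little and settles the choice before the data are seen.

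**What to change.** In section 3.B:

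1. State the fixed effects: period, arm and period-by-arm, alongside the floor and nurse effects.
2. Add patient age and sex, with their coding stated, and any other extracted demographic named in advance, as patient-level fixed effects in each of the 1000 fits, for the primary outcome and the refusal outcome.
3. Keep the model without demographics as a sensitivity analysis.
4. State that adjustment removes only measured mix, so calendar trend and unmeasured severity still limit the before-after conclusion.

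In section 3.A, tabulate patient demographics by period as well as by arm.

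**Cost.** SAP wording and a few model terms, on data already being extracted. The odds ratio becomes conditional on these covariates too. Missing demographic fields need a stated handling rule; a simple missing category can leave some confounding in a non-randomised comparison, so the rule should be chosen with that in mind.

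### Section 3.B models floor and nurse levels only, so if the 21 floors change over time by different amounts, that variation is missing from the standard errors of both change-from-baseline comparisons

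*Combined protocol and SAP*

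**What the plan says.** The unit of randomisation is the floor. Section 2.F states that "Nurses will be cluster randomized by floor to receive one of two education modules about VTE prevention", that "floors were stratified by department (i.e. medicine and surgery) for randomization", and that "Within strata, we will use a coin toss to randomize floors into study arms". Section 2.C covers "All nurses permanently assigned to one of the 21 included study floors".

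Both hypotheses are about change. The primary one expects fewer non-administered doses after either module, "compared with their frequency at baseline". The secondary one is the contrast between arms: "Nurse participants who receive the Dynamic education format will have a larger decrease in frequency of missed doses of VTE prophylaxis". Under section 2.G, data run for a year covering baseline, the education period and the time after it.

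Section 3.B draws one dose per patient at random, repeats this 1000 times, and reports that "we will estimate the odds ratios (ORs) and 95% confidence intervals conditional on the floor and nurse". Floor and nurse are the only levels named. The section gives no floor-by-period term, estimator, reference distribution, degrees of freedom, small-sample method or permutation test.

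**The concern.** A floor intercept describes how a floor differs from the others on average. In a comparison of after with before, that stable difference largely cancels. What remains is how much each floor moved, and floors may move by different amounts for reasons unrelated to the module, such as staffing, case mix or local initiatives.

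A model with floor and nurse intercepts alone treats this movement as if it did not exist. The standard errors of the period effect (primary hypothesis) and the arm-by-period effect (secondary hypothesis) then contain only dose-level sampling noise. The 1000 draws address repeated doses within a patient. Every draw contains the same 21 floors with the same floor-specific shifts, so averaging over draws supplies no information about how variable those shifts are.

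At stake is whether a marginal pre-post result, or a marginal Dynamic-over-Static result, can be taken at its nominal 95% level.

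**Working it through.** The plan states no sample size, power, intracluster correlation or type I error, so there is no figure of its own to reproduce.

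**Inputs from the documents:** 21 floors; two arms; two department strata; coin-toss allocation; change-from-baseline hypotheses; 95% intervals.

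**Assumptions not in the documents:** 400 sampled patients per floor-period; 12% missed doses; floors of equal size; floor-period drift with mean zero and SD τ on the logit scale; an 11:10 or 10:11 split of floors in the simulations.

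**Step 1: drift left out of the model.** The sampling variance of one floor-period log-odds is s² = 1/(n·p·(1−p)) = 1/(400 × 0.12 × 0.88) = 0.0237. A floor's before-after change has true variance 2(s² + τ²), but the intercept-only model assumes 2s². The ratio is 1 + r, with r = τ²/s². The same ratio applies to the mean of all 21 changes and to the difference between arms, so the number of floors cancels. Two-sided type I error with a 1.96 cut-off is 2·Φ(−1.96/√(1+r)).

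| τ | r | √(1+r) | Type I error |
|---|---|---|---|
| 0 | 0 | 1 | 5.0% |
| 0.05 | 0.0025/0.0237 = 0.106 | 1.051 | 6.2% |
| 0.10 | 0.0100/0.0237 = 0.422 | 1.193 | 10.0% |
| 0.15 | 0.0225/0.0237 = 0.950 | 1.397 | 16.0% |

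Simulations agree. Logistic models with floor intercepts (6000 runs, Monte Carlo SE about 0.3 points) gave 5.2% for arm by period and 5.5% for pooled pre-post with no drift, and 6.2% for arm by period at τ = 0.05. A floor-level simulation (20,000 runs) gave 9.8% at 0.10 and 16.2% at 0.15. Neither includes the nurse level or the resampling of doses.

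More patients make it worse, because s² shrinks and τ² does not. At τ = 0.10 the rate is 7.5% with 200 patients per floor-period, 10.0% with 400 and 14.9% with 800.

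**Step 2: would a t cut-off alone repair this?** No. Putting the 18-df value 2.101 in place of 1.96 gives 2·Φ(−2.101/1.193) = 7.8% at τ = 0.10 and 2·Φ(−2.101/1.397) = 13.2% at τ = 0.15. The variance term has to be in the model.

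**Step 3: reference distribution once that variance is modelled.** With department fitted, arm by period has about 21 − 2 − 1 = 18 df. The pooled change has 21 − 1 = 20 df. If floor-by-period variance dominates:

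- 18 df: 2·P(t > 1.96) = 6.6%; the correct cut-off is 2.101, and 2.101/1.960 = 1.072.
- 20 df: 2·P(t > 1.96) = 6.4%; the correct cut-off is 2.086, and 2.086/1.960 = 1.064.
- Maximum-likelihood variances, 18 df: 2·P(t > 1.96 × √(18/21)) = 8.6%.
- Maximum-likelihood variances, 20 df: 2·P(t > 1.96 × √(20/21)) = 7.0%.

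If the variance is nil, the excess disappears. For the pooled change, a 1.96 cut-off with the variance estimate truncated at zero gave 4.3% (maximum likelihood) or 4.1% (REML-type) in simulation.

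**The case against.** The strongest reply is that section 3.B is silent rather than wrong. It does not commit to a 1.96 cut-off and does not say that intercepts are the only random effects. A reader might infer from 21 floors and no stated correction that the 95% intervals are too short and type I error exceeds 5%. The documents do not support that as a fact. They give no reference distribution, intracluster correlation or drift, and with no drift an intercept-only model holds close to 5%.

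A reader might also apply the 6.6% and 8.6% figures directly to the Dynamic versus Static test as planned. That does not follow either. Stable floor differences cancel from a change contrast, so those figures need a post-only comparison, which is not the stated hypothesis, or a model that already estimates floor-by-period variance.

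Nor does random drift bias the arm comparison. Floors are randomised, so drift balances between arms in expectation. The harm is to the standard error, not to the estimate.

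Finally, the title of section 3.B describes a linear model while its text reports odds ratios, so the model must be settled before a degrees-of-freedom method is chosen. Floors per stratum are not given, which makes 18 df approximate.

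All of this stands, and it limits the point to a conditional one. It does not remove it. Floor and nurse are the only structure the plan names, and nothing in the documents shows that drift is negligible. Section 2.F itself cites known differences in practice and culture between medical and surgical floors, although that says nothing about their size within a department or over time.

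**Conclusion.** The point holds in conditional form. Followed as written, with floor and nurse intercepts only, the analysis leaves floor-by-period variation out of the standard errors for both hypotheses. Under the assumed 400 patients per floor-period and 12% missed doses, type I error runs from about 5% with no drift to about 6%, 10% and 16% at drift SDs of 0.05, 0.10 and 0.15. The reference distribution is the lesser issue. It adds up to about 1.4 to 1.6 percentage points with REML-type variances (3.6 with maximum likelihood on 18 df), and only once the variance is modelled and is large.

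The drift SDs and patient numbers are assumptions, and the result depends on them. The calculation takes drift to average zero across floors. A trend common to all floors is a separate question for the pre-post comparison, and this change would not resolve it. The point is a cheap improvement to the analysis, not evidence that the planned intervals are invalid.

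**What to change.** In section 3.B:

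1. State the model and estimator, and reconcile the linear label with the odds ratios.
2. Add a floor-by-period random effect, or analyse the 21 floor-level changes directly.
3. Base intervals and p-values on a t distribution with between-floor degrees of freedom: about 18 for arm by period with department fitted, and 20 for the pooled pre-post change.
4. Check Dynamic versus Static with a permutation test that re-randomises floors by the coin-toss scheme actually used within medicine and surgery.

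This needs SAP wording and some programming on data already to be collected. The price is width: about 7% from the t reference alone. With drift, intervals widen by roughly 1.072 × √(1+r), which is about 13%, 28% and 50% at drift SDs of 0.05, 0.10 and 0.15 under the same assumptions. If floors do not drift, the mixed-model route is conservative. In a two-arm floor-level simulation with a REML-type variance and a t cut-off on 19 df, type I error was 2.9% at zero floor variance and 4.9% to 5.0% once that variance at least equalled the sampling variance. A t test on the floor-level changes holds about 5% with or without drift.

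### The nurse survey is tested with a plain Chi-squared test that ignores the randomised floors, so its p-values can be too small

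*Combined protocol and SAP*

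**What the plan says.** The design in section 2.A is a "Cluster randomized trial". Section 2.F names the unit: "Nurses will be cluster randomized by floor to receive one of two education modules about VTE prevention". Floors are stratified by department (medicine or surgery), and "Within strata, we will use a coin toss to randomize floors into study arms". Section 2.E gives the number of clusters: "All nurses permanently assigned to one of the 21 included study floors will be included in this study". Section 2.D adds: "The same education type will be assigned to all nurses on a single floor to mitigate issues related to contamination if nurses discuss the education".

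The survey is described in section 2.H. After finishing the module, "nurses will be asked to complete a voluntary 5-question survey to assess the relevance of and satisfaction with the education module". It is the first secondary outcome listed.

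Its analysis is a single line in section 3.B.b.ii: "Nurse-reported relevance of and satisfaction with the education modules will be analyzed using a two-sided Chi-squared test". For the dose data, section 3.B recognises the multilevel structure and promises that "we will estimate the odds ratios (ORs) and 95% confidence intervals conditional on the floor and nurse".

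**The concern.** An ordinary Chi-squared test takes each nurse's answer as independent of every other. Under floor-level assignment, any tendency of nurses on a floor to answer alike passes straight into the difference between arms, and the test's variance leaves it out. Comparing nurse-level answers is legitimate; the defect is the unadjusted variance.

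The treatment of the dose data does not help. It works by drawing one dose per patient and modelling given floor and nurse, so it has no counterpart for a survey of nurses. The survey line also sits under the mixed-model heading of section 3.B, but it names its own, different test, so the heading supplies no adjustment.

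Positive correlation is plausible: the plan itself keeps one module per floor because nurses may talk to each other about it. What is at stake is a false finding that nurses prefer the Dynamic or the Static format, which could influence which platform is adopted.

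**Working it through.** The plan states no sample size, ICC, respondent count or significance level for the survey, so it has no figure to reproduce.

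**Inputs from the plan**
- 21 floors, two arms, stratified by department (sections 2.E and 2.F).
- One module per floor (section 2.D).
- Voluntary survey of individual nurses (section 2.H).
- Two-sided Chi-squared test (section 3.B.b.ii).

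**Assumptions**
- Two-sided 5% level, in line with the 95% intervals planned for the doses.
- *m* = 5 to 40 respondents per floor and ICC 0 to 0.10.
- The test compares the two arms. The plan does not say so in words, but it is the natural reading.

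**Step 1: formula, equal respondents per floor**

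Design effect DE = 1 + (m − 1) × ICC. Actual type I error = 2 × [1 − Φ(1.96/√DE)].

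Example, m = 20 and ICC 0.05: DE = 1 + 19 × 0.05 = 1.95; 1.96/√1.95 = 1.40; type I error = 0.160. The 21 × 20 = 420 respondents then carry the information of 420/1.95 ≈ 215, and a naive p-value of 0.01 corresponds to about 0.065.

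| m | ICC 0 | 0.01 | 0.05 | 0.10 |
|---|---|---|---|---|
| 5 | 0.050 | 0.055 | 0.074 | 0.098 |
| 10 | 0.050 | 0.060 | 0.104 | 0.155 |
| 20 | 0.050 | 0.072 | 0.160 | 0.250 |
| 40 | 0.050 | 0.096 | 0.254 | 0.376 |

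**Step 2: simulation of the same 16 settings**

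Beta-binomial answers; 11 medicine and 10 surgery floors assumed; arms balanced within department; agreement rate 0.7; 10,000 runs each. The plain Chi-squared test agrees with the table to within 0.006 (for example 0.076 at m = 5, ICC 0.05; 0.154 at m = 20, ICC 0.05; 0.374 at m = 40, ICC 0.10). A floor-level regression on arm and department, tested on 21 − 3 = 18 degrees of freedom, has type I error between 0.046 and 0.054 in all 16.

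**Step 3: where the correlation lies (m = 20, ICC 0.05)**

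| Share of correlation between departments | Plain test, arms balanced within department | Plain test, each floor tossed independently |
|---|---|---|
| 0 | 0.165 | 0.160 |
| 50% | 0.105 | 0.161 |
| 100% | 0.050 | 0.164 |

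The floor-level test stays between 0.049 and 0.051 throughout.

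**Step 4: unequal respondents per floor**

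Mean 20, coefficient of variation (CV) about 0.55, ICC 0.05: DE ≈ 1 + [(1 + 0.55²) × 20 − 1] × 0.05 = 1 + 25.05 × 0.05 = 2.25, giving type I error of about 0.19. Simulation with 7, 11 or 14 medicine floors (8,000 runs) gives 0.187 to 0.194 for the plain test and 0.049 to 0.050 for the floor-level test.

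**The case against.** The strongest reply is that positive correlation within floors is not enough by itself. If the coin toss balances arms within each department and all of the correlation is a medicine–surgery difference, the plain test keeps its 5% (step 3). The one source of heterogeneity that the plan names is a department difference, and it concerns prophylaxis practice rather than opinions of a training module. This stands as a condition on the consequence. It does not rescue the test, because the plan does not say that the toss balances arms, and balance does nothing for correlation between floors of the same department.

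The evidence for such correlation is indirect. The contamination sentence explains the allocation, not the similarity of ratings, and the survey follows completion at once, which limits discussion in between. Still, nurses have three months to complete the module, so earlier finishers can talk to later ones.

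The size is wholly assumed. A voluntary survey may yield few answers per floor: at m = 5 and ICC 0.01 the error is only 5.5%, and 38% needs both extremes. That is fair, and the range should be read that way.

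Two lesser points are that the plan does not exclude a cluster-adjusted Chi-squared test, and that neither hypothesis concerns satisfaction. On the first, the line names no adjustment, so an analyst following it would run the ordinary test. The second limits the importance of the point, not its correctness.

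**Conclusion.** The concern holds. The survey test as written does not match the floor-randomised design. Its p-values are too small whenever answers are positively correlated within floors beyond what a balanced department split absorbs; if floors are tossed independently, a department difference inflates the error as well.

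The omission is certain; its size is not known. Under the stated assumptions the true error of a nominal 5% test is 5% at ICC 0, about 7% at 5 respondents per floor and ICC 0.05, and about 16% at 20 per floor and the same ICC (about 19% with uneven response). It reaches 38% only at 40 per floor and ICC 0.10. The 16% falls to about 10.5% if arms are balanced within department and half the correlation lies between departments. The problem is confined to one secondary outcome and should be corrected before the survey is analysed.

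**What to change.** Replace the line in section 3.B.b.ii with a floor-level analysis. For each survey item, regress the floor's proportion of favourable answers, or its mean score, on arm and department, and test arm with a t distribution on 18 degrees of freedom (fewer if a floor has no respondents). State in advance how each item is scored, since the plan does not describe the response scale.

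A mixed logistic or ordinal model with a random floor effect, fixed department and a named small-sample correction, for example between-within degrees of freedom, is an acceptable alternative. The essential point is that both floor and department are accounted for and that the method suits 21 clusters.

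The cost is one SAP sentence and a little analysis work, with no new data. P-values will generally be less favourable, and an unweighted floor-level test loses some power if respondents per floor vary widely.
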